1.2 Study Organization

The name and contact information of the responsible party and individuals involved with the study (e.g., investigator(s), sponsor's medical expert and study monitor, sponsor's representative(s), laboratories, steering committees, and oversight committees [including ethics committees (ECs)], as applicable) will be maintained by the sponsor and provided to the investigator.

2. SERIOUS ADVERSE EVENT REPORTING

The investigator will comply with applicable laws/requirements for reporting serious adverse events (SAEs) to the sponsor and/or ECs, as applicable.

ALL SAEs, INCLUDING SUSARs, ARE TO BE REPORTED ON THE ADVERSE EVENT ELECTRONIC CASE REPORT FORM (eCRF) WITHIN 24 HOURS AFTER BECOMING AWARE OF THE EVENT. IF THE eCRF IS NOT AVAILABLE THEN THE SAE MUST BE REPORTED ON THE SERIOUS ADVERSE EVENT REPORT (SAER) FORM AND TRANSMITTED TO THE SPONSOR TO MEET THE 24 HOUR TIMELINE REQUIREMENT.

**Drug Safety contact information: see SAE Report Form
Refer to SAE Protocol Sections and the study team roster for further information.**

For definitions and information on the assessment of these events, refer to the following:

- AE, Section [13.2](#)
- SAE, Section [13.2.1.1](#)
- SUSARs, Section [13.2.1.2](#)
- Assessment of AEs, Section [13.2.4](#)

3. SYNOPSIS

INVESTIGATIONAL PRODUCT	
Name of Investigational Product (IP)	BAX 855
Name(s) of Active Ingredient(s)	Pegylated full-length Recombinant Factor VIII
CLINICAL CONDITION(S)/INDICATION(S)	

 Treatment and prophylaxis of bleeding in severe Hemophilia A 	
PROTOCOL ID	261303
PROTOCOL TITLE	Phase 3, prospective, randomized, multi-center clinical study comparing the safety and efficacy of BAX 855 following PK-guided prophylaxis targeting two different FVIII trough levels in subjects with severe Hemophilia A
Short Title	BAX 855 PK-guided Dosing
STUDY PHASE	Ph3
PLANNED STUDY PERIOD	
Initiation	First subject in: Q4 2015
Primary Completion	Q2 2018
Study Completion	Q4 2018
Duration	3 years
STUDY OBJECTIVES AND PURPOSE	
Study Purpose	

 To compare the efficacy and safety of pharmacokinetic (PK)-guided treatment with BAX 855 targeting FVIII trough levels of 1-3% and approximately 10% (8-12%) To further characterize PK and pharmacodynamic (PD) parameters of BAX 855 	
Primary Objective	

 The primary objective is to compare 2 prophylactic dosing regimens of BAX 855 targeting 2 different FVIII trough levels, by comparing the proportions of subjects achieving a total annualized bleeding rate (ABR) of 0 in the second 6-month study period 	
Secondary Objectives	
Efficacy: 
 To compare the 2 prophylactic dosing regimens of BAX 855 targeting 2 different FVIII trough levels with respect to the following: 
 The proportion of subjects in each prophylactic dosing arm achieving a spontaneous ABR and spontaneousⁱ joint bleeding rate (AJBR) of 0 in the second 6-month study period The proportion of subjects in each prophylactic dosing arm with a total, spontaneous ABR and AJBR <2 	

ⁱ i.e., not trauma related.


 ➤ The total, spontaneous, and trauma-related ABRs in the 12-month study period ➤ The reduction in ABR between the 2 treatment arms and the historical ABR prior to study enrollment ➤ The total weight-adjusted consumption of BAX 855 for each prophylactic regimen ➤ The joint status using the Hemophilia Joint Health Score (HJHS) and over time ➤ Health-related quality of life (HRQoL) and pharmacoeconomic outcomes (including Short form-36 questionnaire [SF-36], EuroQol-5 dimension [EQ-5D], Haemo-SYM, and healthcare resource utilization) 
 • To determine the hemostatic efficacy of BAX 855 in the control of bleeding episodes • To evaluate the efficacy of BAX 855 for perioperative management, if surgery is required 
Safety:
 
 • To determine the immunogenicity of BAX 855 • To determine the safety of BAX 855 
Pharmacokinetics:
 
 • To determine the PK parameters of BAX 855 at baseline and steady state, if applicable, and the correlation with pre-infusion VWF antigen level • To determine incremental recovery (IR) over time 
Patient Reported Outcomes
 
 • To assess the difference in the SF-36 physical domain and component change scores from baseline to follow-up between subjects in the 10% trough arm and subjects in the 1-3% trough arm • To assess the difference in the change of days of physical activity participation from baseline to follow-up between subjects in the 10% trough arm and subjects in the 1-3% trough arm 
Exploratory Objectives:
 
 • To determine the potential correlation between thrombin generation assay (TGA) parameters, FVIII trough levels and ABR • To assess the change in bleed and pain severity scores as measured by the Haemo-SYM questionnaire • To assess the change in HRQoL using EQ-5D and mental domain and component score of the SF-36 • To assess the difference in the change in healthcare resource utilization from baseline to follow-up between subjects in the 10% trough arm and subjects in the 1-3% trough arm

STUDY DESIGN	
Study Type/ Classification/ Discipline	Efficacy, Pharmacokinetic, Safety including Immunogenicity, and Pharmacodynamic
Control Type	Dose-Response
Study Indication Type	Prevention, Treatment
Intervention Model	Parallel design
Blinding/Masking	Open label

Study Design	This study is a Phase 3, prospective, randomized, open-label, multicenter study to compare the safety and efficacy of a PK-guided BAX 855 treatment regimen targeting 2 different FVIII trough levels in approximately 116 subjects with severe hemophilia A to have 96 subjects evaluable (48 per treatment arm).
Planned Duration of Subject Participation	The subject's participation will last approximately 15-16 months and is based on the assumption that completion of screening procedures will require approximately 6 weeks; PK assessments, dose calculation and randomization will take 6-8 weeks and the treatment period from the baseline visit to study completion will be 12 months.
Primary Outcome Measure 1. Presence or absence of any bleedings in the second 6-month study period	
Secondary Outcome Measures Efficacy 
 1. Total, spontaneous, and traumatic ABR, and spontaneous AJBR 2. Total weight-adjusted consumption of BAX 855 3. Overall hemostatic efficacy rating at 8 (\pm1) hours after the initiation of treatment and at resolution of bleed 4. Number of BAX 855 infusions needed for the treatment of bleeding episodes 5. HJHS 6. Intra-, post- and perioperative hemostatic efficacy in case of surgery 7. Intra- and postoperative blood loss in case of surgery Safety 
 1. Occurrence of adverse events (AEs) and serious adverse events (SAEs) 2. Clinically significant changes in vital signs and clinical laboratory parameters (hematology, clinical chemistry, and lipids) 3. Inhibitory antibodies to FVIII, and binding antibodies to FVIII, BAX 855, polyethylene glycol (PEG), and Chinese Hamster Ovary (CHO) protein Patient Reported Outcomes (PROs) 
 1. Physical domain and component scores of the SF-36 Health Survey Pharmacokinetics 
 1. BAX 855 PK parameters based on FVIII activity at baseline and steady state, if applicable: 
 a. AUC_{0-∞} (area under the plasma concentration versus time curve from time 0 to infinity), IR at 15-30 minutes post-infusion, T_{1/2} (plasma half-life), MRT (mean residence time), CL (clearance), maximum plasma concentration (C_{max}) and time to maximum concentration in plasma (T_{max}), V_{ss} (Volume of distribution at steady state) b. IR over time 	

Exploratory Outcome Measures	

 1. Thrombin generation assay (TGA) parameters (lag time, time to peak thrombin generation, peak thrombin generation, and endogenous thrombin potential [ETP]) 2. Bleed and pain severity scores as measured by the Haemo-SYM questionnaire 3. HRQoL as assessed using EQ-5D and mental domain and component scores of the SF-36 4. Healthcare resource utilization 	
INVESTIGATIONAL PRODUCT(S), DOSE AND MODE OF ADMINISTRATION	
Active Product	
BAX 855 Dosage form: injection, powder, lyophilized, for solution
 
Dose and Dosage frequency: BAX 855 dose will be PK-guided to maintain FVIII target trough levels of 1-3% or approximately 10% (8-12%) at the following dosing frequencies: FVIII trough levels of 1-3%: approximately twice weeklyⁱⁱ FVIII trough levels of approximately 10% (8-12%): every other dayⁱⁱⁱ
 
Mode of Administration: intravenous bolus

SUBJECT SELECTION	
Targeted Accrual	Approximately 116 subjects will be enrolled to have 96 subjects evaluable (48 in each prophylaxis dosing arm).
Number of Groups/ Arms/Cohorts	2

Inclusion Criteria for Subjects Transitioning from Another BAX 855 study:
 
 1. Subject has completed the end of study visit of a BAX 855 study or is transitioning from the ongoing Continuation Study 261302 2. Subject is either receiving on-demand or prophylactic treatment with BAX 855 and had an ABR of ≥ 2 documented and treated during the past 12 months 3. Subject is human immunodeficiency virus negative (HIV-); or HIV+ with stable disease and CD4+ count ≥ 200 cells/mm³, as confirmed by central laboratory 4. Subject is willing and able to comply with the requirements of the protocol 
Inclusion Criteria for Newly Recruited Subjects:
 
 1. Subject is 12 to 65 years old at the time of screening 2. Subject has severe hemophilia A (FVIII clotting activity <1%) as confirmed by central laboratory OR by historically documented FVIII clotting activity performed by a certified clinical laboratory, optionally supported by a FVIII gene mutation consistent with severe hemophilia A 3. Subject has been previously treated with plasma-derived FVIII concentrates or recombinant FVIII for ≥ 150 documented EDs 	

ⁱⁱ Twice weekly: infusion on day 3 or 4, at 2 different doses to cover the different treatment intervals, or every 3.5 days. According to individual PK, frequency may be adjusted based on FVIII trough levels.

ⁱⁱⁱ Depending on subject's individual PK, frequency may be adjusted.

4. Subject is either receiving on-demand treatment or prophylactic treatment and had an annual bleeding rate of ≥ 2 documented and treated during the past 12 months
5. Subject has a Karnofsky performance score of ≥ 60 at screening
6. Subject is HIV-; or HIV+ with stable disease and CD4+ count ≥ 200 cells/mm³, as confirmed by central laboratory at screening
7. Subject is hepatitis C virus negative (HCV-) by antibody (if positive, additional PCR testing will be performed), as confirmed by central laboratory at screening; or HCV+ with chronic stable hepatitis
8. If female of childbearing potential, subject presents with a negative urine pregnancy test and agrees to employ adequate birth control measures for the duration of the study
9. Subject is willing and able to comply with the requirements of the protocol

Exclusion Criteria

Exclusion Criteria for Subjects Transitioning from Another BAX 855 study:

1. Subject has developed a confirmed inhibitory antibody to FVIII with a titer of ≥ 0.6 Bethesda Units (BU) using the Nijmegen modification of the Bethesda assay as determined at the central laboratory during the course of the previous BAX 855 study
2. Subject has been diagnosed with an acquired hemostatic defect other than hemophilia A
3. The subject's weight is < 35 kg or > 100 kg
4. Subject's platelet count is $< 100,000$ /mL
5. Subject has an abnormal renal function (serum creatinine > 1.5 times the upper limit of normal)
6. Subject has active hepatic disease with alanine aminotransferase (ALT) and/or aspartate aminotransferase (AST) levels ≥ 5 times the upper limit of normal
7. Subject is scheduled to receive a systemic immunomodulating drug (e.g., corticosteroid agents at a dose equivalent to hydrocortisone greater than 10 mg/day, or α -interferon) other than anti-retroviral chemotherapy during the study
8. Subject has a clinically significant medical, psychiatric, or cognitive illness, or recreational drug/alcohol use that, in the opinion of the investigator, would affect subject's safety or compliance
9. Subject is planning to take part in any other clinical study during the course of the study
10. Subject is a member of the team conducting this study or is in a dependent relationship with one of the study team members. Dependent relationships include close relatives (i.e., children, partner/spouse, siblings, parents) as well as employees of the investigator or site personnel conducting the study

Exclusion Criteria for Newly Recruited Subjects

1. Subject has detectable FVIII inhibitory antibodies (≥ 0.6 BU using the Nijmegen modification of the Bethesda assay) as confirmed by central laboratory at screening
2. Subject has a history of confirmed FVIII inhibitors with a titer ≥ 0.6 BU (as determined by the Nijmegen modification of the Bethesda assay or the assay employed with the respective cut-off in the local laboratory) at any time prior to screening
3. Subject has been diagnosed with an inherited or acquired hemostatic defect other than hemophilia A (e.g., qualitative platelet defect or von Willebrand's disease)

4. The subject's weight is <35 kg or >100 kg
5. Subject's platelet count is <100,000/mL
6. Subject has known hypersensitivity towards mouse or hamster proteins, PEG or Tween 80
7. Subject has severe chronic hepatic dysfunction (e.g., ≥ 5 times upper limit of normal ALT and/ or AST, as confirmed by central laboratory at screening, or a documented INR >1.5)
8. Subject has severe renal impairment (serum creatinine >1.5 times the upper limit of normal)
9. Subject has current or recent (<30 days) use of other pegylated drugs prior to study participation or is scheduled to use such drugs during study participation
10. Subject is scheduled to receive during the course of the study, a systemic immunomodulating drug (e.g., corticosteroid agents at a dose equivalent to hydrocortisone greater than 10 mg/day, or α -interferon) other than anti-retroviral chemotherapy
11. Subject has participated in another clinical study involving an IP or investigational device within 30 days prior to enrollment or is scheduled to participate in another clinical study involving an IP or investigational device during the course of this study
12. Subject has a medical, psychiatric, or cognitive illness or recreational drug/alcohol use that, in the opinion of the investigator, would affect subject safety or compliance
13. Subject is a member of the team conducting this study or is in a dependent relationship with one of the study team members. Dependent relationships include close relatives (i.e., children, partner/spouse, siblings, parents) as well as employees of the investigator or site personnel conducting the study.

STATISTICAL ANALYSIS

Sample Size Calculation

For the sample size assessment the following assumptions were used: Approximately 40% of subjects in BAX 855 regimen targeting 1-3% trough level are expected to be bleed free as shown in the ADVATE Prophylaxis study and the BAX 855 pivotal study 261201. For the BAX 855 regimen targeting approximately 10% (8-12%) trough level, an increase to 70% bleed-free subjects is expected based on modeling the bleeding rates per FVIII level in the BAX 855 pivotal study 261201.

Under these assumptions 48 subjects per study group are needed to reject the null hypothesis of no difference between the study arms against a 2-sided alternative at the 5% level of statistical significance with 80% power. Assuming a drop-out rate of close to 10%, and 10-15% of subjects being non-compliant, approximately 116 subjects are planned to be randomized between the 2 BAX 855 regimens with an allocation ratio of 1:1.

Planned Statistical Analysis

The proportion of subjects with ABR = 0 in the 2 prophylaxis treatment regimens in the second 6 months period will be compared using a chi-square test with continuity correction at a 2-sided 5% level of significance. For all outcome measures, bleeding rates will be analyzed using a negative binomial model and descriptive statistics will be presented for the 2 dosing regimens for other outcomes. Point estimates (mean or median) and 95% confidence intervals will be computed if feasible.

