6.4.2 Findings from Clinical Studies

To date, 3 clinical studies have been completed:

- Study 261101 is a first in human study to assess the safety and PK of BAX 855 in PTPs aged 18-65 years with severe hemophilia A with ≥ 150 EDs to FVIII products, conducted in Europe and Japan. A total of 24 subjects were enrolled; 19 were treated and 18 were evaluable for PK analysis. Nine were treated with 30 IU/kg (Cohort 1) and 10 were treated with 60 IU/kg (Cohort 2) of BAX 855, including 2 subjects from Japan. BAX 855 appeared to be safe and well tolerated after a single dose administration and no subject developed inhibitors to FVIII or binding antibodies to PEG. The mean plasma half-life ($T_{1/2}$) was 1.4- and 1.5-fold higher for BAX 855 compared to ADVATE in Cohorts 1 and 2, respectively, demonstrating prolonged circulation of BAX 855 compared to ADVATE. These data support the use of the BAX 855 dosing regimens planned in this study.

- Study 261201 is a Phase 2/3 study in which BAX 855 was found to be safe and well tolerated in all 137 treated subjects. None of the subjects developed inhibitory antibodies to FVIII of ≥ 0.6 BU/mL or persistent binding antibodies to FVIII, PEG-FVIII, PEG, or CHO proteins. The study confirmed the results of the Phase 1 study 261101, demonstrating that BAX 855 extends the mean $T_{1/2}$ by approximately 1.4-fold and MRT by approximately 1.5-fold as compared to ADVATE. Twice weekly prophylactic infusions at the intended dose of 45 ± 5 IU/kg BAX 855 resulted in an ABR which was significantly lower than that observed with on-demand treatment with a prophylaxis/on-demand ABR ratio of 0.10. Approximately 40% of subjects treated on prophylaxis did not experience any bleeding episodes, while all subjects treated on-demand experienced bleeding episodes. BAX 855 was efficacious in the treatment of bleeding episodes with 96.1% rated excellent or good and 95.9% treated with 1 or 2 infusions. This study demonstrated that BAX 855 is safe and efficacious in treating bleeding episodes and in prophylaxis administered twice weekly in adults and adolescents ≥ 12 years with severe hemophilia A.

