8. STUDY DESIGN

8.1 Brief Summary

This study is a Phase 3, prospective, randomized, open-label, multicenter study to compare the safety and efficacy of a PK-guided BAX 855 treatment regimen targeting 2 different FVIII trough levels of 1-3% and approximately 10% (8-12%) in adolescent and adult PTPs with severe hemophilia A (<1% FVIII). Enrolled subjects will undergo an initial PK assessment following a single administration of BAX 855 to determine the subject's individual PK parameters to tailor the dose for the targeted FVIII trough levels. Subjects will be randomized to one of 2 study arms of 58 subjects each, to target trough FVIII levels of 1-3% or approximately 10% (8-12%), for a treatment period of 12 months. An optional repeat PK at steady state will be performed after 9 months of treatment.

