8.2 Overall Study Design

This study is a Phase 3, prospective, randomized, open-label, multicenter study to compare the safety and efficacy of PK and FVIII trough level-guided BAX 855 treatment targeting FVIII trough levels of 1-3% or approximately 10% (8-12%) in a total of 96 evaluable (48 in each of 2 study arms) adolescent and adult PTPs with severe hemophilia A (<1% FVIII). Approximately 116 subjects will be enrolled for a total of 96 evaluable subjects (assuming a dropout rate of close to 10% and 10-15% of subjects being non-compliant). Subjects from the BAX 855 continuation (261302) the BAX 855 surgery (261204) study, the BAX 855 pediatric (261202) study^v, and newly recruited subjects including BAX 855-naïve subjects will participate.

Subjects will be screened per protocol inclusion/exclusion criteria and, following confirmation of eligibility, will undergo an initial PK assessment following a single administration of BAX 855 (60 ±5 IU/kg) to determine PK parameters. Following the PK assessment, subjects will be randomized to one of 2 dosing regimens: the standard treatment arm will target FVIII trough levels of 1-3% and the second, intensified treatment arm will target trough levels of approximately 10% (8-12%) FVIII. The dose and frequency will be based on each subject's individual PK. More frequent dosing should be considered if single doses of >80 IU/kg are required or regular FVIII peak levels of 200% would be reached.

^v In case subject is at least 12 years of age at the time of informed consent of this study.

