10. STUDY PROCEDURES

10.1 Informed Consent and Enrollment

Any subject, or their legal representatives, as required, who provides informed consent (i.e., signs and dates the informed consent form and assent form, if applicable) is considered enrolled in the study.

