10.3 Screening and Study Visits

The study site is responsible for maintaining an enrollment/screening log that includes all subjects enrolled. The log also will serve to document the reason for screening failure. If a subject does not satisfy all screening criteria, the same subject may be re-screened at a later date. A complete or partial re-screen may also become necessary at the discretion of the investigator or sponsor. All screening data will be collected and reported in eCRFs, regardless of screening outcome. For the purpose of analysis, only the data from the most recent screening visit will be used. If a subject is re-screened, the End of Study CRF should be completed, and a new ICF, new SIC and new CRF are required for that subject.

The screening procedures including laboratory evaluations must be completed within 56 days or repeated if more than 56 days have elapsed. Exemptions may be granted for administrative reasons, e.g., delay in timely availability of laboratory results.

The overall study design is illustrated in the [Figure 1](#). Details on the procedures to be performed at each study visit, including screening, can be found in [Section 21.2 Detailed Flow Diagram of Study Procedures](#), [Section 21.3 Schedule of Study Procedures and Assessments](#), and [Section 21.4 Clinical Laboratory Assessments](#). Only explanatory details are provided in the following section.

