4. ANALYSIS SETS

4.1 All Subjects Enrolled Set (ENR)

The all subjects enrolled set (ENR) is to contain all subjects that signed informed consent.

Information on whether a subject signed informed consent is obtained from the *Informed Consent* electronic case report form (eCRF) panel.

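### Targeted Accrual and Protocol 8.2 set 116 subjects at consent, but the sample size plans about 116 randomised; the two agree only if nobody is lost before randomisation

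*Protocol*

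**What the plan says.** The number 116 appears with two different units.

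- **Counted at enrolment.** Protocol Synopsis, Targeted Accrual: "Approximately 116 subjects will be enrolled to have 96 subjects evaluable (48 in each prophylaxis dosing arm". Protocol 8.2: "Approximately 116 subjects will be enrolled for a total of 96 evaluable subjects".
- **Meaning of enrolled.** Under Protocol 10.1, any subject "who provides informed consent (i.e., signs and dates the informed consent form and assent form, if applicable) is considered enrolled in the study". SAP 4.1 agrees: "The all subjects enrolled set (ENR) is to contain all subjects that signed informed consent". SAP 6.1 derives enrolment from the presence of a consent date.
- **Counted at randomisation.** The Synopsis sample-size paragraph says "approximately 116 subjects are planned to be randomized between the 2 BAX 855 regimens"; Protocol 14.1.1 and SAP 2.3 repeat it. Protocol 8.1 gives the split: "Subjects will be randomized to one of 2 study arms of 58 subjects each".

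The Synopsis row on study design gives 116 subjects with no unit.

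The step from 96 to 116 is explained by drop-out near 10% and non-compliance of 10–15%. No other loss is named. Randomisation follows the PK assessment (Protocol 8.5). The Synopsis expects about 6 weeks for screening and a further 6–8 weeks for PK, dose calculation and randomisation, so about 12–14 weeks in all. Section 10.3 keeps a log of screening failures, and section 10.6 lists screen failure as a reason for discontinuation.

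**The concern.** With the protocol's own definition of enrolled, the two targets are the same only if every subject who consents is randomised. The protocol plans for screening failures, so it does not expect that. A site or recruitment manager who reads Targeted Accrual together with section 10.1 could close recruitment at 116 consents. The shortfall against 58 per arm would come on top of the post-randomisation losses that the allowance was meant to absorb. At stake are the planned 48 evaluable per arm and, if the loss is large enough, the stated 80% power.

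**Working it through.** **Inputs.** Bleed-free proportions 40% and 70%, two-sided 5% level, 80% power, 48 per arm, 116 randomised 1:1 (Protocol 14.1.1). The primary test is the chi-square with continuity correction, analysed by intention to treat with multiple imputation (Protocol 14.4.1). The pre-randomisation loss *s* is not given in the documents, so the values below are assumptions.

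**Reproducing 48 per arm.**

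- Without correction: n0 = [1.960·√(2·0.55·0.45) + 0.842·√(0.4·0.6 + 0.7·0.3)]² / 0.3² = 41.97.
- With correction: n = (n0/4)·[1 + √(1 + 4/(n0·0.3))]² = 48.4, or 49 rounded up.
- Exact enumeration of the corrected test at 48 per arm gives 80.05% power.

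The stated 48 is sound, and 80% power is tied to 48 per arm, not to 58.

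**If 116 is counted at consent.**

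- Randomised = 116·(1 − s).
- Evaluable, keeping the plan's ratio 96/116, = 96·(1 − s).

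Arms are rounded to the nearest whole subject. Power is exact, with the continuity-corrected normal approximation in brackets.

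| Loss s | Randomised | Per arm | Power, all randomised | Evaluable | Per arm | Power, evaluable only |
|---|---|---|---|---|---|---|
| 0% | 116 | 58 | 87.6% (87.6%) | 96 | 48 | 80.0% (79.6%) |
| 5% | 110.2 | 55 | 84.6% (85.5%) | 91.2 | 45 or 46 | 75.3% or 77.0% (76.5% or 77.6%) |
| 10% | 104.4 | 52 | 85.4% (83.2%) | 86.4 | 43 | 73.7% (74.2%) |
| 17% | 96.3 | 48 | 80.0% (79.6%) | 79.7 | 40 | 72.5% (70.4%) |
| 21% | 91.6 | 46 | 77.0% (77.6%) | 75.8 | 38 | 68.1% (67.7%) |

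Exact power moves in small steps because the counts are whole numbers, which is why 52 per arm shows slightly more than 55.

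**Where the intent-to-treat analysis falls below 80%.** It needs 48 per arm, so 116·(1 − s) = 96 and s = 1 − 96/116 = 17.2%. At 47 per arm exact power is 78.5%.

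**Consents needed to randomise 116.** 116/(1 − s): 116/0.95 = 122.1, so 123; 116/0.90 = 128.9, so 129; 116/0.80 = 145.

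**The case against.** The strongest reply is that this is loose wording for one intended number. The sample-size text and section 8.1 say randomised, and section 8.2 attaches to its 116 the same drop-out and non-compliance allowance that section 14.1.1 attaches to 116 randomised. No section says that recruitment stops at 116 consents. This is probably what the sponsor means, but enrolled is a defined term in both documents and the field that sets accrual uses it. The intended meaning should be stated.

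Three stronger readings are tempting and are not supported.

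- **That the trial necessarily misses 80% power.** The primary analysis does not drop non-compliers, and it imputes bleeds for early leavers who provide no data. On randomised numbers, power stays at about 80% or more up to about 17% loss. The lower figures apply only to the evaluable count.
- **That about 21% will be lost.** Section 6.4.2 reports of the first-in-human study: "A total of 24 subjects were enrolled; 19 were treated and 18 were evaluable for PK analysis". That is 5 of 24 (21%) untreated, but the text does not say why. Here transitioning subjects may reuse end-of-study assessments for screening (10.3.1), and those who need no new PK go straight to randomisation and Baseline (21.2). The 21% row is only an illustration.
- **That re-screened subjects count twice.** On re-screening, "a new ICF, new SIC and new CRF are required for that subject", but section 10.3 still treats the person as the same subject, and nothing says that accrual is counted by subject code.

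A further reply is that the stated losses, taken literally, already leave only about 87 to 94 of 116 evaluable (116·0.75 = 87; 116·0.9·0.9 = 94). That is a separate question about the allowance. Correcting the word enrolled does not settle it.

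**Conclusion.** The inconsistency is real and sits in the text that sets the accrual target. Read with the protocol's own definition, 116 enrolled cannot yield 116 randomised unless nobody is lost between consent and randomisation, and no allowance is made for such loss. The sample-size calculation itself reproduces.

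The effect on power is conditional. If 96/116 of randomised subjects are evaluable, even a small loss takes the count below 48 per arm, with power of about 75–77% at 5% loss and about 74% at 10%. If all randomised subjects are analysed as the primary analysis specifies, exact power falls below 80% only beyond about 17% loss, and is 77% at 21%.

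These figures assume that the 40% and 70% proportions hold without dilution by non-compliance. The intent-to-treat figures also assume that every randomised subject starts prophylaxis, as the Full Analysis Set requires, and that imputation costs no information.

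**What to change.** - In the Synopsis (Targeted Accrual) and Protocol 8.2, replace *enrolled* with *randomized*. In the Synopsis row on study design, add *randomized* to the 116 subjects. Recruitment then continues until about 116 subjects, 58 per arm, are randomised.
- State the expected number of consents as 116/(1 − assumed pre-randomisation loss), with the assumed rate: for example about 129 at 10%.
- If accrual is in fact meant to stop at 116 consents, restate the number to be randomised and the resulting power instead.

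The cost is a wording change. It adds no randomised subjects beyond those section 14.1.1 already plans. If recruitment had been run to 116 consents, it would mean more screening, about 13 further consents at 10% loss (129 − 116).
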